22.9 EXPLORATORY ENDPOINTS

The following list of secondary endpoints will be analyzed using the mITT population and will be summarized based on the type of data: Continuous (CONT), Binary (BIN) or Correlation (CORR):

- Montgomery–Åsberg Depression Rating Scale (MADRS) response rate at all follow-up time points (CONT)
- Montgomery–Åsberg Depression Rating Scale Self-report (MADRS-s) scores of the two arms (response and remission rates) at all time points (CONT)
- Hamilton Anxiety Rating Scale (HAM-A) at all time points (CONT)
- Young Mania Rating Scale (YMRS) at all time points (CONT)
- tDCS Adverse Events Questionnaire (AEQ) at 10 and 20 weeks (CONT)
- HDRS-17 (CONT), MADRS (CONT), MADRS-s mean decrease (CONT), remission (BIN), and response rate (BIN) at 6 weeks comparison between groups.
- HDRS-17 (CONT), MADRS (CONT), MADRS-s (CONT) at 20 weeks (after open-label)
- Correlation between MADRS and MADRS-s. (CORR)
- Correlation between the percent of sessions using the FLOW FL-100 and HDRS-17/MADRS decrease in the active group at 10 weeks.
- The within-patient clinically meaningful improvement as defined as at least -3 points on the HDRS-17 scale. The percentage of subjects for each arm that reaches -3 points or more improvement and also the Cumulative Distribution Function Curves of Change in HDRS-17 Score from Baseline to Primary end-point by arm.

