22.8 SECONDARY EFFECTIVENESS ENDPOINTS

Secondary effectiveness endpoints will be analyzed descriptively.

For continuous variables (CONT), results will be summarized with the numbers of observations, means, standard deviation, median, minimums and maximums. Differences between the two groups, where specified, will be summarized with the differences of the two means, and 95% confidence intervals for the difference between the means. These calculations will be done under the assumption that data for the two groups are independent and approximately normally distributed. The confidence interval for the difference of two means will be calculated under the assumption of unequal variances. If the asymptotic assumptions fail, then nonparametric summary statistics (medians, 25th and 75th percentile) may be displayed as an alternative.

For binary variables (BIN), results will be summarized with patient counts, percentages/rates. Differences between the two groups, where specified, will be summarized with the difference in percent and the Newcombe score 95% confidence interval for the difference of two percentages.

For correlation analysis, Spearman correlation will be used to assess the association between two continuous variables. The correlation coefficient and the 95% confidence intervals will be reported.

CONFIDENTIAL Page **61** of **69**

There are three secondary endpoints controlled multiplicity (see below):

- The mean change in points for MADRS score from baseline to Week 10. This will be evaluated using the same statistical methodology as the primary endpoint.
- Clinical Response will be analyzed as a responder endpoint. Clinical Response is defined as a >50% reduction from the baseline HDRS-17 or MADRS score, MADRS-s at Week 10.
- Remission will be analyzed as a responder endpoint where remission is defined as an HDRS-17 score ≤7 or a MADRS score ≤10). The endpoint will be tested using a two-group large-sample normal approximation test of proportions with a one-sided 0.025 considered significant.
- Quality of life improvement as measured by EQ-5D-3L in the active compared to sham arm at week 10 compared to baseline.

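### Section 22.9 tags MADRS response and MADRS-s response and remission rates as continuous although they are yes/no outcomes, and gives the AEQ only a continuous summary (minor)

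*Protocol*

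**What the plan says.** Protocol section 22.9 states that the listed endpoints "will be summarized based on the type of data: Continuous (CONT), Binary (BIN) or Correlation (CORR"), so the tag decides the method. The methods are in section 22.8:

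- **CONT:** "results will be summarized with the numbers of observations, means, standard deviation, median, minimums and maximums". Where a group difference is specified, it is the difference of two means with a 95% interval that allows unequal variances.
- **BIN:** counts and percentages. Where a group difference is specified, it is "the difference in percent and the Newcombe score 95% confidence interval for the difference of two percentages".

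Four entries in section 22.9 matter here:

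- MADRS: "response rate at all follow-up time points (CONT").
- MADRS-s: "scores of the two arms (response and remission rates) at all time points (CONT").
- All three depression scales, ending: "MADRS-s mean decrease (CONT), remission (BIN), and response rate (BIN) at 6 weeks comparison between groups".
- AEQ: "tDCS Adverse Events Questionnaire (AEQ) at 10 and 20 weeks (CONT").

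Section 22.8 defines clinical response as a reduction of more than half from baseline and remission as a score at or below a cut-off. It calls both responder endpoints.

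**The concern.** A response or remission rate is built from one yes or no per participant. Because the tag selects the method, a wrong tag is a wrong instruction to whoever programs the tables. Section 22.9 also disagrees with itself: response and remission are BIN in the 6-week bullet and CONT in the bullets that cover all time points. The BIN bullet does not settle the matter, because the schedule has visits at Weeks 1, 4, 7, 10 and 20 and none at Week 6.

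Two things are at stake. First, a normal-theory interval on 0/1 data behaves poorly when events are very rare, as they might be at the first follow-up visits. Second, a mean AEQ score does not show how many participants had headache, a burning sensation or skin redness. Those are among the ten anticipated events in section 19.1, and section 19 has their frequency and severity captured by the AEQ rather than on the adverse event forms.

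**Working it through.** **1. The tags side by side**

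| Outcome | Nature | Section 22.8 | Section 22.9, all time points | Section 22.9, 6 weeks |
|---|---|---|---|---|
| MADRS response | yes/no | responder endpoint | CONT | BIN |
| MADRS-s response | yes/no | responder endpoint | CONT | BIN |
| MADRS-s remission | yes/no | no cut-off given for this scale | CONT | BIN |
| MADRS-s score | numeric | – | CONT, same bullet as the rates | CONT |

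**2. Inputs for the size of the effect**

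The plan states no figure for these endpoints, so only the arm sizes can be taken from it. Section 22.2 reproduces. The pooled SD is sqrt((7.1² + 7.9²)/2) = 7.51. A two-sample t-test for a difference of 3.2 at one-sided 0.025 has 80.2% power at 88 per arm (176 in all) and 87.6% at 108 per arm (216). Then 216/0.80 = 270. The arm sizes used are therefore 216/2 = 108 (after attrition) and 270/2 = 135 (all randomised, closer to an early visit). The response rates are assumptions, because the protocol gives none for early visits.

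**3. The two intervals**

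With p₁ = x₁/n and p₂ = x₂/n:

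- CONT: p₁ − p₂ ± t × sqrt(p₁(1−p₁)/(n−1) + p₂(1−p₂)/(n−1)), with Welch degrees of freedom.
- BIN (Newcombe): with Wilson limits (l, u) for each arm, lower = d − sqrt((p₁−l₁)² + (u₂−p₂)²) and upper = d + sqrt((u₁−p₁)² + (p₂−l₂)²), where d = p₁ − p₂.

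Example, 3/108 vs 1/108: p₁ = 2.78%, p₂ = 0.93%, d = 1.85 points.

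- CONT: standard error 1.84, t = 1.974, so 1.85 ± 3.63, that is −1.78 to 5.48.
- BIN: Wilson limits are 0.95% to 7.85% and 0.16% to 5.06%. Lower = 1.85 − sqrt(1.83² + 4.13²) = −2.67. Upper = 1.85 + sqrt(5.07² + 0.77²) = 6.98.

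Widths in percentage points at 108 per arm:

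| Responders | CONT | BIN |
|---|---|---|
| 0 vs 0 | 0 | 6.9 |
| 1 vs 0 | 3.7 | 7.7 |
| 3 vs 1 | 7.3 | 9.7 |
| 5 vs 2 | 9.5 | 11.3 |
| 11 vs 5 | 14.1 | 14.9 |
| 27 vs 16 | 21.4 | 21.2 |

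**4. Exact coverage of the nominal 95% interval**

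Coverage is summed over all pairs of binomial outcomes. The last columns give the chance that the CONT interval has zero width. For example, at 1% vs 0.5% and 108 per arm, (0.99 × 0.995)^108 = 19.7%.

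| True rates | CONT, 108 | BIN, 108 | CONT, 135 | Zero width, 108 | Zero width, 135 |
|---|---|---|---|---|---|
| 1% vs 0.5% | 79.5% | 99.9% | 86.0% | 19.7% | 13.1% |
| 2% vs 1% | 87.8% | 99.0% | 92.7% | 3.8% | 1.7% |
| 3% vs 1% | 94.4% | 98.0% | 94.9% | 1.3% | 0.4% |
| 5% vs 2% | 94.4% | 96.7% | 94.9% | 0.04% | 0.01% |
| 10% vs 5% | 95.0% | 96.0% | 95.0% | 0 | 0 |

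The shortfall also needs the rates to differ. At equal rates the CONT interval is not short of coverage: 99.7% at 0.5% in each arm (108 per arm), and 97.5% at 1% and 95.5% at 2% in each arm (135 per arm).

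**5. The AEQ**

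Section 19 records unanticipated events on the adverse event forms and sends anticipated ones to the AEQ. Section 22.14 plans per-subject incidence of specific events, with numbers and percentages of subjects affected, but does not name the AEQ as a source. The only analysis entry that names the AEQ is the CONT line in section 22.9.

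**The case against.** The best reply has four parts.

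- **The interval may never be produced.** Section 22.8 gives a group difference only where one is specified. The MADRS response bullet specifies none, and in the MADRS-s bullet a comparison is at most implied. Without an interval, CONT gives a mean, and the mean of a 0/1 variable is the response rate. This stands, and it limits the harm.
- **Early response may not be that rare.** A reader might infer that intervals at early visits will be too narrow or collapse to zero. The documents do not support that without conditions: they give no early rates, and the problem needs unequal rates of about 2% or lower or, for zero width, no variation in either arm.
- **The labels are partly defensible.** A reader might infer that MADRS remission is also tagged continuous; it is not. The MADRS-s bullet mixes scores, for which CONT is right, with rates, so it is ambiguous as well as mistagged.
- **Symptom incidence is planned.** A reader might infer that it is never tabulated. Section 22.14 does plan per-subject incidence, and the adverse event definition in section 19.1 covers anticipated events. What remains is narrower: the anticipated events are collected through a different instrument, and no passage says that it feeds those tables. The AEQ form and its scoring are not shown, so a numeric summary is not wrong in itself.

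The fallback in section 22.8 (medians and quartiles if asymptotic assumptions fail) does not rescue the CONT tag. With fewer than 25% responders, the median and both quartiles of a 0/1 variable are all zero.

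**Conclusion.** The mistagging is real. It contradicts section 22.8 and another bullet of the same list. Its numerical effect is conditional: coverage of about 79-88% at 108 per arm, or 86-93% at 135 per arm, if the true rates are unequal and about 2% or lower in both arms, and if an interval is produced at all. From about 3-5% upward the effect is negligible. The rates are assumptions of this check.

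For the AEQ, the supported conclusion is that n (%) by symptom is not assured by the text, not that it is absent from the plan.

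These outputs are exploratory and descriptive. The primary test and the multiplicity-controlled secondary tests do not depend on them, so this is a minor point.

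**What to change.** In section 22.9:

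- Tag MADRS response and MADRS-s response and remission as BIN at every visit, with counts, percentages and the Newcombe interval for group differences.
- Split the MADRS-s bullet, so that the score is listed separately as CONT.
- Report each AEQ symptom as n (%) per arm with severity categories at Weeks 10 and 20, and keep any total score as a supplement. State in section 22.14 how the AEQ relates to the incidence tables.

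The cost is a few words in the protocol and some table shells. No new data are needed.

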⁷ Five sessions per week for 3 weeks, followed by three sessions per week for 7 weeks. In total, thirty-six sessions during 10 weeks during the blinded phase. Please refer to Table 2 and Table 3 below for more details.

⁸ In case there is an early termination the research staff can request to have an early termination interview, if the subject agrees.

⁹ Diagnostic Assessment for MDD will be performed by Investigator-Psychiatrist according to the most recent APA Practice Guideline for treatment of MDD.

	1011011 301	icuule uulli	ig billiaca	pridoc.						
Week	1	2	3	4	5	6	7	8	9	10
Number of sessions	5	5	5	3	3	3	3	3	3	3

Table 2. Stimulation schedule during blinded phase.

Table 3. Stimulation schedule during open-label phase.

Week	Previous assignm ent	1	2	3	4	5	6	7	8	9	10
Number of	Active	3	3	3	3	3	3	3	3	3	3
sessions	Sham	5	5	5	3	3	3	3	3	3	3

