11.7 EXPLORATORY ENDPOINTS

- Young Mania Rating Scale (YMRS) at 10 weeks.
- tDCS Adverse Events Questionnaire (AEQ) at 10 and 20 weeks
- Hamilton Anxiety Rating Scale (HAM-A) change at week 10.

- HDRS-17, MADRS, MADRS-s mean decrease, and remission and response rate at 20 weeks (after open-label) compared to open-label start and baseline.
- Correlation between MADRS and MADRS-s.
- Correlation between adherence to stimulation and HDRS-17/MADRS decrease in the active group at 10 weeks.
- Neuropsychological measure: verbal learning (Rey Auditory Verbal Learning Test (RAVLT) and information processing speed (Symbol-Digit Modalities Test (SDMT)
- Treatment acceptability questionnaire (TAQ) as developed by UEL. There is one form at baseline and another at week 10 and 20.
- The within-patient clinically meaningful improvement as defined as at least -3 points on the HDRS-17 scale. The percentage of subjects for each arm that reaches -3 points or more improvement and also the Cumulative Distribution Function Curves of Change in HDRS-17 Score from Baseline to Primary end-point by arm.

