15.4 WITHDRAWALS

Participants have the right to withdraw from the clinical investigation at any time and for any reason. The Principal Investigator will ask the reason for their withdrawal and will record all information regarding the participant discontinuation.

A Participant may be withdrawn from the clinical investigation for the following reasons:

- Participants may choose to withdraw from the clinical investigation under the terms of the Declaration of Helsinki and their consent documentation without having to give a reason;
- Any unanticipated adverse event which, in the opinion of the Principal Investigator, is related to the treatment and will endanger the well-being of the participant if treatment is continued;
- Development of any intercurrent illness(es), infection or condition(s) that might interfere with the clinical investigation;
- Non-compliance with the clinical investigation procedures deemed by the Principal Investigator to be sufficient to cause discontinuation;
- Any problem deemed by the Investigator to be sufficient to cause discontinuation.

Participants will be withdrawn from the trial if they do not comply with the intervention, namely if they are unable to have a minimum of 60% of the tDCS session (22 (660 minutes) out of 36 sessions at week 10) during the blinded phase, or if they develop serious adverse effects from any part of the study. Recording of the reasons for withdrawal will be made. Their GP will be informed about their withdrawal, and they will have a telephone follow up at 1 month following their withdrawal.

If a participant is withdrawn, their device is disabled to make sure they cannot continue the treatment.

Regardless of the reason for withdrawal, data available for the participant at the time of withdrawal, including the reason for withdrawal, will be entered on the Case Report Forms. The research staff will request to have an optional early termination visit to collect the same data as at the week 10 and week 20 interview. The Principal Investigator will treat all participants discontinued from the investigation due to an unanticipated adverse event, directly related to the investigation, until the reaction resolves. A participant that has been withdrawn from the study after treatment start will not be replaced.

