18 CONCOMITANT MEDICATIONS/THERAPIES

For the purposes of this clinical study, only medications taken or administered for the following will be recorded *(Ensure medications reflected in incl/excl are listed here)*:

- Muscle relaxation;
- Other medications related to or given for the participant's MDD.

19 Adverse Event & Device Deficiency Reporting

Subjects will be carefully monitored during the study for possible adverse events (AEs) from the time they sign the Informed Consent Form to the time of study completion. All medical events and conditions prior to this time point are to be captured as medical history.

Any observed unanticipated AE will be fully investigated by the Investigator and classified in line with the definitions of ISO 14155:2020 below. The frequency and severity of anticipated AEs will instead be captured using the tDCS Adverse Events Questionnaire (AEQ).

All unanticipated adverse events that occur during this study will be recorded on the adverse event eCRFs and must include the following information at minimum:

- Event Description
- Date of Onset
- Date of Resolution
- Severity
- Seriousness
- Relationship to Study Device/Procedure
- Outcome

Adverse events will be reported and classified by the Investigator using the specific signs, symptoms or abnormal laboratory values, or medical diagnosis if no signs, symptoms, or abnormal laboratory values can be identified.

Significant new information and updates should continue to be captured in the subject's records and in the EDC as they become available and the adverse event should be followed until it is resolved or no further improvement is expected, or the subject is lost to follow-up.

Adverse events that meet the definitions of seriousness in Section 19.1 below should also be reported to the Sponsor per the instructions provided in Section 19.2.4 below.

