19.2.4 SAE REPORTING

Flow Neuroscience AB is responsible for the classification and reporting of adverse events and ongoing safety evaluation of the clinical investigation in line with ISO 14155:2020 and US/UK regulatory requirements.

Investigator will report "to the Sponsor, without unjustified delay, all serious adverse events and device deficiencies that could have led to a serious adverse device effect; this information shall be promptly followed by detailed written reports" [ISO 14155:2020 § 9.8 b]. Device malfunctions and use errors should also be reported without unjustified delay.

In the event of becoming aware of any SAE (including all device deficiencies), anticipated or unanticipated, the Investigator will report the event to Flow Neuroscience AB and Curebase immediately (at least within 24 hours after first knowledge of the event) by entering SAE information in the EDC. In the event the EDC is unavailable for any reason, notification to Flow Neuroscience AB should be made via email as follows:

Sponsor Contact: [name] E-mail: [contact] [contact]

The Investigator should provide additional information on the SAE by updating the information in the EDC as updates become available. Flow Neuroscience AB may also ask for additional clinical reports including redacted source documents to be provided by the Investigator to assist in the assessment of the event. Significant new information and updates should continue to be submitted promptly to and entered in the EDC as they become available, and the Investigator should follow the SAE until it is resolved, or no further improvement is expected.

It is the responsibility of each Investigator to report all SAEs and/or SADEs to the IRB/EC, according to national regulations and IRB/EC requirements. A copy of the IRB/EC report should be

CONFIDENTIAL Page **54** of **69**

forwarded to Flow Neuroscience AB. In countries that require the Sponsor to report safety events rather than investigators, the Sponsor (Flow Neuroscience AB) will report SAEs and/or SADEs to the EC.

Flow Neuroscience AB will ensure that all SAEs and device deficiencies that could have led to a SAE are reported to the Competent Authorities in accordance with European Medical Devices directives and all applicable national regulations.

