22.2 SAMPLE SIZE ASSUMPTIONS AND CALCULATIONS

The sample size calculation is based on data from Brunoni et al (2017). The calculation is based on a two- sample t-test for mean difference with the following assumptions:

- Group difference in means = 3.2
- Standard deviation of Investigational and Sham groups = 7.1 and 7.9, respectively
- One-sided type I error = 0.025
- 80% power

The resulting sample size is 176 subjects. To obtain an increase in statistical power (87.6%), 216 subjects were chosen. Accounting for 20% attrition, the overall sample size will be 270 subjects.

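### The AEQ is the only systematic record of non-serious anticipated adverse events, but its summary is fixed at Weeks 10 and 20 and has no place for the AEQ collected at early termination

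*Protocol*

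**What the plan says.** **Capture.** The opening of protocol section 19 separates two routes. For the eCRF: "All unanticipated adverse events that occur during this study will be recorded on the adverse event eCRFs". For anticipated events: "The frequency and severity of anticipated AEs will instead be captured using the tDCS Adverse Events Questionnaire (AEQ". Section 19.1 lists the anticipated events, among them headache, scalp pain, burning sensation and skin redness. Serious events follow their own route whether anticipated or not (19.2.4: "In the event of becoming aware of any SAE (including all device deficiencies), anticipated or unanticipated").

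**Collection times.** Table 1 marks the AEQ at Week 10, Week 20 and early termination. Sections 13.4 and 13.5 list it at Weeks 10 and 20, and 13.3 does not list it at Weeks 1, 4 and 7. Section 15.4 describes an "optional early termination visit to collect the same data as at the week 10 and week 20 interview". A footnote to Table 1 makes clear that this depends on consent: "In case there is an early termination the research staff can request to have an early termination interview, if the subject agrees".

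**Analysis.** Section 11.7 and the synopsis give the endpoint as "tDCS Adverse Events Questionnaire (AEQ) at 10 and 20 weeks". Section 22.9 repeats it, marked continuous, in the mITT set: "tDCS Adverse Events Questionnaire (AEQ) at 10 and 20 weeks (CONT". The same list analyses HAM-A and YMRS at every time point.

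**Early discontinuation.** Section 15.6 says that data previously collected from participants who withdraw, are discontinued or are lost to follow-up enter the analysis and the study report. Section 22.14 presents dropout data separately with a discussion of bias, and plans a listing of AEs among early discontinuations. Section 22.3.2 assigns all safety and tolerability summaries to the As Treated (AT) set.

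**The concern.** For a participant who stops before Week 10, the early-termination AEQ is the only AEQ completed after treatment began. Section 13.1 also lists an AEQ at screening, but that precedes stimulation and cannot record device effects. Because the endpoint is tied to Weeks 10 and 20, this record does not enter the AEQ comparison between arms, even when it has been collected.

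At stake is how completely the ordinary side effects of the device are described. The planned AEQ comparison is conditional on staying to Week 10, and staying may depend on tolerability. Section 24.4 says the data are to support a premarket application, so the side-effect profile bears on the benefit-risk case.

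**Working it through.** **1. The plan's own figure.** Section 22.2: "Accounting for 20% attrition, the overall sample size will be 270 subjects". Check: 216 / (1 - 0.20) = 270. So 270 - 216 = 54 participants are expected to be lost, or 27 per arm if losses are equal.

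**2. Which record covers whom.**

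| Participant | AEQ after treatment start | Used in the 11.7 / 22.9 AEQ summary? |
|---|---|---|
| Reaches Week 10 | Week 10 | Yes |
| Leaves before Week 10, attends termination visit | Early termination | No time point given |
| Leaves before Week 10, declines or cannot be reached | None | Nothing to use |

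**3. Formula.** Let a be the share who stop early, r_c the AEQ result in completers and r_d the result in early stoppers.

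All-participant result minus completer-only result = a x (r_d - r_c).

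If only a fraction f of early stoppers give an AEQ, the weight a becomes w = a f / (1 - a + a f). With a = 0.20:
- f = 1: w = 54/270 = 0.200
- f = 0.5: w = 27/243 = 0.111
- f = 0.25: w = 13.5/229.5 = 0.059

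**4. Scenarios.** The protocol gives no AEQ rates, so those below are assumptions. Completer rate 20%; entries are the change in percentage points when early-termination AEQs are added.

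| Rate in early stoppers | All respond | Half respond | A quarter respond |
|---|---|---|---|
| 40% (twice) | +4.0 | +2.2 | +1.2 |
| 30% (1.5 times) | +2.0 | +1.1 | +0.6 |
| 20% (equal) | 0 | 0 | 0 |
| 10% (half) | -2.0 | -1.1 | -0.6 |

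With completer rates from 10% to 50%, the same ratios and full response, the range is -5.0 (0.20 x (25% - 50%)) to +10.0 (0.20 x (100% - 50%)).

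**5. Continuous scale.** Section 22.9 summarises the AEQ as continuous. The same formula holds for means: with all early stoppers responding, each point of difference in mean score between early stoppers and completers moves the mean by 0.2 points.

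**6. Between arms.** The bias in the arm difference is a_active x (r_d - r_c)_active minus a_sham x (r_d - r_c)_sham. It vanishes if the two products are equal.

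**7. Analysis set.** Section 22.9 puts the AEQ in mITT, while 22.3.2 puts every safety and tolerability summary in AT. AT needs one treatment and analyses by treatment received; mITT also drops participants randomised in error and analyses by assignment. The two statements do not agree for the AEQ.

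**The case against.** The strongest reply is that nothing in the protocol excludes these records. Section 15.6 brings in data from participants who stop early, 22.14 reports dropouts separately and discusses bias, and the AT set does not require completion. Mapping a termination record to an analysis visit is ordinary SAP work, and the SAP is not shown. Much of this stands: a reader might infer that early-termination AEQs are discarded, and the documents do not support that. It does not close the gap, because a separate presentation leaves the between-arm AEQ comparison restricted to those who reach the visit. The restriction is also written into the protocol in three places, beside two scales analysed at every time point, so it is not merely a detail left open.

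A second reply is that AEs are reviewed at every visit and the reason for each discontinuation is documented, so a participant who stops for burning or headache should leave a trace. That is fair, and the listing of AEs in early discontinuations may pick up some of it. Section 19 nevertheless assigns the frequency and severity of anticipated events to the AEQ, so these other traces are not systematic.

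A third reply concerns direction. A reader might infer that side-effect rates are understated, most of all in the active arm. The documents do not show this. Early stoppers have shorter exposure and could report fewer events. Some stop for reasons unrelated to tolerability, such as technical failure (15.1) or a rise in HDRS-17 (15.2). Section 9.1 states that tolerability and dropout are equal between sham and active in the literature. Also, the 22.9 line yields means; incidence rates belong to 22.14, which carries no Week 10 or Week 20 limit. This reply stands in full.

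**Conclusion.** The point holds in a limited form. The protocol collects an AEQ at early termination but gives it no role in the AEQ comparison, which therefore describes only participants who reach Week 10 or Week 20. The text needs reconciling with 15.6, 22.14 and 22.3.2.

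The size is 0.20 times the difference between early stoppers and completers. It is zero if they are alike and reverses if early stoppers report less. This assumes that the planned 20% attrition all occurs before Week 10; the rates in the scenarios are illustrative. Neither understatement of side effects nor a difference in bias between arms is established. Because the visit is optional, only part of any gap can be recovered by a change of analysis. No figure in the protocol changes, and the primary endpoint is unaffected.

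**What to change.** In the synopsis, 11.7 and 22.9:

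- Define the blinded-phase AEQ result as the Week 10 AEQ or, for a participant who left before Week 10, the early-termination AEQ.
- Report it by arm, with the number from each source and the number with no AEQ, and show the Week-10-only summary alongside.
- Put Week 20 AEQs, and early-termination AEQs after Week 10, in a separate open-label table.
- Use the AT set, as 22.3.2 requires, in place of mITT.
- Add a cross-reference to 15.6 and 22.14, so that it is clear how the separate dropout presentation relates to this summary.

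The cost is wording in three places and one derived variable, with no new data. There are two drawbacks. An early-termination AEQ reflects less than 10 weeks of exposure, which is why source counts and the Week-10-only summary should be shown. Some early stoppers will still have no AEQ, and that number should be stated by arm.
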